positive human immunodeficiency virus (HIV) antibody, or active syphilis (positive treponema pallidum particle agglutination assay [TPPA] with positive rapid plasma reagin [RPR] test);

- History of allergic reactions to hUC-MSC-sEVs, hyaluronidase, or excipients in the study drug;
- Known atopic diathesis (e.g., severe asthma, urticaria requiring systemic treatment);
- Nasal structural abnormalities or lesions that affect drug delivery (e.g., severe nasal septal deviation, nasal polyps, chronic sinusitis with acute exacerbation);
- Cerebrospinal fluid rhinorrhea (spontaneous or post-traumatic);
- Participation in other interventional clinical trials within 3 months prior to screening;
- Unwillingness or inability to comply with protocol-specified procedures (e.g., refusal to undergo required imaging examinations);
- Pregnant or lactating women (confirmed by urine pregnancy test for women of childbearing potential); women of childbearing potential who cannot or refuse to use effective contraceptive measures (e.g., combined oral contraceptives, intrauterine device) during the study and for 3 months after the last dose;
- Uncontrolled psychiatric disorders (e.g., schizophrenia, major depressive disorder with suicidal ideation) that affect compliance;
- Other conditions deemed unsuitable for enrollment by the investigator (e.g., terminal illness with life expectancy <6 months).

(3) Records of Failed Screening

- Investigators are responsible for all subjects who have signed the informed consent form, regardless of whether they are ultimately enrolled.
- If a subject is deemed ineligible during screening (at the first visit), the investigator shall complete the "Screening Failure Form" (attached to the CRF) and document the specific reason for failure (e.g., "NIHSS score = 4 < 6", "History of mechanical thrombectomy"). The screening number assigned to the ineligible subject shall not be reused.

(4) Criteria for Determining Lost-to-Follow-Up Subjects

A subject is considered lost to follow-up if:

- They experience an AE, SAE, or other complication that requires study termination and urgent treatment, as judged by the investigator;

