- Their condition of a concurrent disease (excluding the index stroke) deteriorates, requiring alternative treatment that conflicts with the study protocol; if the subject's stroke condition deteriorates after receiving hUC-MSC-sEV-001 (e.g., progression of neurological deficit), they shall withdraw from the study and be classified as an invalid case (not a lost-to-follow-up case);
- They have poor compliance (e.g., missed ≥ 2 scheduled visits, refusal to undergo required assessments) or express unwillingness to continue the study;
- They are lost to contact for ≥ 2 weeks despite repeated attempts (e.g., telephone, text message, home visit).

For lost-to-follow-up subjects, the investigator shall make every effort to complete the final safety assessment (e.g., vital signs, adverse event recording) and document the reason for withdrawal in the CRF.

(5) Provisions for Excluded Cases

A case is excluded from the efficacy analysis set if:

- The subject is misdiagnosed (e.g., final diagnosis is transient ischemic attack rather than ischemic stroke);
- The subject meets the inclusion criteria but is not administered any dose of hUC-MSC-sEV-001, or fails to receive scheduled doses due to production failure of the study drug;
- The subject participates in another interventional clinical trial during the study period;
- The subject receives prohibited combined medications (e.g., antineoplastic drugs, neurotrophic factors) or non-protocol-specified treatments that affect efficacy assessment;
- The subject has no evaluable efficacy data (e.g., no post-baseline NIHSS or mRS assessment);
- The subject has severe protocol violations (e.g., administration of the wrong dose, missed ≥ 3 doses).

Excluded cases shall be documented in the "Protocol Deviation Log", and their CRFs shall be retained for audit. Subjects who receive at least one dose of the study drug and have safety data shall be included in the safety analysis set.

(6) Criteria for Terminating or Withdrawing from the Study

i. Study Termination

Study termination refers to the early cessation of the entire study before completion of the planned protocol. The decision to terminate the study shall be made by the sponsor, principal investigator, or Ethics Committee, and shall be documented in the "Study Termination Report". Reasons for termination include:

- Emergence of SAEs that suggest a causal relationship with the study drug and pose a serious risk to subjects;

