- Confirmation of the MTD or identification of an unsafe dose level;
- Major flaws in the study design that affect data validity;
- Regulatory requirements (e.g., request by the National Medical Products Administration [NMPA]).

. Subject Withdrawal

Subjects may withdraw from the study at any time for the following reasons:

(1) Investigator-determined withdrawal:

① The subject develops a medical condition that makes continued participation unsafe (e.g., severe allergic reaction, intracranial hemorrhage);② The subject uses medications that interact with the study drug (e.g., immunosuppressants) or affect efficacy assessment (e.g., edaravone);③ The subject experiences a SAE that requires termination of study participation;④ The subject has poor compliance that compromises the reliability of safety or efficacy data.

(2) Subject-initiated withdrawal:

① The subject voluntarily requests to withdraw (no reason required);② The subject is lost to follow-up (no contact for ≥ 2 weeks).

For withdrawn subjects, the investigator shall conduct a final safety assessment (if possible) and document the reason for withdrawal in the CRF. Subjects who withdraw due to AEs/SAEs shall receive appropriate medical treatment, and follow-up shall continue until the AE/SAE resolves or stabilizes.

(7) Criteria for Terminating the Study

The study will be terminated immediately if any of the following occurs:

≥ 2 subjects experience DLT at the same dose level (indicating that the dose exceeds the MTD);

- Production of hUC-MSC-sEV-001 fails to meet quality standards for 3 consecutive batches, resulting in inability to administer scheduled doses;

- The study drug is found to have no clinical benefit (e.g., no improvement in neurological function in all enrolled subjects) or is associated with unexpected severe toxicity;
- A major protocol deviation is identified (e.g., incorrect randomization, unapproved dose modification) that invalidates the study results;
- The sponsor terminates the study due to funding, strategic adjustments, or other reasons;
- The Ethics Committee or NMPA issues an order to terminate the study.

3. Intervention Measures

(1) Trial Drug

- **Generic Name:** Human Umbilical Cord Mesenchymal Stromal Cell-Derived Small Extracellular Vesicle (hUC-MSC-sEV-001) Nasal Drops
- **Source:** Isolated and purified from the supernatant of hUC-MSCs cultured under GMP conditions

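### Section 2(4) classes a subject whose participation ends because of an AE or SAE as lost to follow-up, while section 2(6) calls an SAE of this kind an investigator-determined withdrawal and keeps lost to follow-up for loss of contact

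*Protocol*

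**What the plan says.** Protocol section 2(4) opens with "A subject is considered lost to follow-up if" and gives four grounds:

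- **AE or SAE:** "They experience an AE, SAE, or other complication that requires study termination and urgent treatment, as judged by the investigator".
- **Concurrent disease:** "Their condition of a concurrent disease (excluding the index stroke) deteriorates", so that treatment conflicting with the protocol is needed.
- **Compliance or willingness:** poor compliance, or the subject no longer wishes to continue.
- **Loss of contact:** "They are lost to contact for ≥ 2 weeks despite repeated attempts".

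For all four, the investigator is to try to complete a last safety assessment and to "document the reason for withdrawal in the CRF".

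Section 2(6), under subject withdrawal, sorts departures into two groups. The investigator-determined group includes "The subject develops a medical condition that makes continued participation unsafe (e.g., severe allergic reaction, intracranial hemorrhage") and "The subject experiences a SAE that requires termination of study participation". It also includes poor compliance. The subject-initiated group holds voluntary withdrawal and "The subject is lost to follow-up (no contact for ≥ 2 weeks"). A closing paragraph says that subjects who withdraw because of AEs or SAEs are treated and then followed until the event has resolved or is stable.

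**The concern.** Loss to follow-up normally means that the site no longer knows how the subject is doing. A subject taken out for an SAE and given urgent treatment is in the opposite position: the site knows the outcome and knows why the subject left. Section 2(6) uses the term in its normal sense and section 2(4) does not.

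This is a 3+3 dose-escalation study whose primary endpoint is toxicity. How many subjects stopped because of an adverse event, and at which dose, is something any reader of the report will look for. If site staff code from 2(4), those subjects fall into the same category as subjects who could not be reached. The mislabel also lands on the subjects who matter most: section 2(6) gives severe allergic reaction and intracranial hemorrhage as its examples of unsafe conditions, and section 5(1) names anaphylactic reaction and symptomatic intracranial hemorrhage in its DLT definition.

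**Working it through.** There is no figure to reproduce. The check sets the two sections side by side.

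| Reason for leaving | Label in 2(4) | Label in 2(6) |
|---|---|---|
| SAE that ends participation | Lost to follow-up | Investigator-determined withdrawal, item 3 |
| Condition that makes continuing unsafe | Lost to follow-up, if urgent treatment is needed | Investigator-determined withdrawal, item 1 |
| Non-serious AE that ends participation | Lost to follow-up | Not in either list; the closing paragraph treats it as a withdrawal |
| Worsening concurrent disease | Lost to follow-up | Not named; may fall under item 1 or 2 |
| Poor compliance | Lost to follow-up | Investigator-determined withdrawal, item 4 |
| Unwilling to continue | Lost to follow-up | Subject-initiated, voluntary |
| No contact for at least 2 weeks | Lost to follow-up | Subject-initiated, lost to follow-up |

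The sections give the same label only in the last row. The contradiction is explicit for SAEs, unsafe conditions, poor compliance and unwillingness. For non-serious AEs and concurrent disease, 2(6) has no listed category of its own, but its definition of loss to follow-up still excludes them, because contact has not been broken.

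**One reading assumption.** The AE ground in 2(4) speaks of study termination, which section 2(6)(i) defines as stopping the whole study. Applied to a single subject, it can only mean the end of that subject's participation, and it is read that way here.

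**A case followed through.** Suppose a subject has a Grade 4 allergic reaction after the second dose, judged related and serious, and is treated urgently.

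1. Section 5(1): this is a DLT.
2. Sections 3(4) and 8(3): the subject withdraws, and under 8(3) follow-up continues.
3. Section 2(6): investigator-determined withdrawal, followed until the event has resolved or is stable.
4. Section 2(4): lost to follow-up, with an effort at a last safety assessment.

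Steps 2 and 3 agree. Step 4 does not, and a subject under continuing follow-up cannot sensibly carry its label.

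**Scale.** Section 1(2) enrols 3 subjects per dose, or 6 after expansion. One subject is 1/3 = 33% or 1/6 = 17% of the cohort. These are shares of a cohort, not estimates of how often the case will arise.

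**The case against.** The best defence is that 2(4) is a general drop-out list with a poor title. Loss of contact is only one of its four grounds, so the category is plainly meant to be wider than its name. The reason for leaving is recorded in the CRF for every subject in it, so the adverse event can be recovered. None of the safety endpoints in section 5 (DLT, drug-related SAEs, mortality, laboratory abnormalities) is calculated from a disposition label. Section 8(6) requires all AEs to be followed until they settle, whatever the subject's label, which largely closes the gap between the follow-up duties in 2(4) and 2(6).

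Most of this stands, and it rules out three stronger readings that a reader might infer:

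- **That toxicity is hidden.** Section 2(4) asks for the reason and for adverse event recording, and sections 2(5) and 11(1) keep dosed subjects in the safety set.
- **That the subject would be counted as a subject-initiated loss of contact.** Section 2(4) says neither thing about the AE ground. That reading joins the label of one section to the definition of the other. Nor does the protocol contain a disposition table from which a count of AE discontinuations would come out as zero.
- **That the subject drops out of the DLT count.** Nothing in the document makes a lost-to-follow-up subject non-evaluable or replaceable. The protocol is silent on subjects who leave before day 14, but this label does not create that gap.

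The defence does not remove the contradiction. The same term has two definitions in one protocol, and staff have to choose between them when a subject leaves. A CRF that records an AE as the reason and loss to follow-up as the category contradicts itself. Nor is this a matter to leave to an analysis plan, since the protocol fixes both rules itself.

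**Conclusion.** The point holds as an internal contradiction in current text. A subject whose participation ends because of an SAE or an unsafe condition is lost to follow-up under 2(4) and an investigator-determined withdrawal under 2(6), with a lighter follow-up duty stated in 2(4) than in 2(6). Applied literally, 2(4) misclassifies AE-driven discontinuations in a trial small enough for one subject to be a third of a cohort.

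The damage is to disposition reporting and to clarity for the site. It does not extend to a demonstrated loss of AEs or DLTs. The conclusion rests on reading study termination in 2(4) as the end of one subject's participation. Because a rule is wrong rather than merely unspecified, and the remedy is wording, it should be corrected before the first subject is enrolled.

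**What to change.** Reconcile 2(4) with 2(6) as follows:

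1. In 2(4), keep loss of contact for at least 2 weeks as the only ground for loss to follow-up, matching 2(6).
2. Move the AE/SAE ground to investigator-determined withdrawal, worded to cover non-serious AEs as well. Move the concurrent-disease ground there too, since 2(6) does not now name it. The clause inside that ground that labels stroke deterioration an invalid case needs its own reconciliation with the NIHSS criterion in section 5(1) when it is moved.
3. Delete the compliance and willingness ground from 2(4), since 2(6) already covers both parts.
4. Make discontinuation due to AE/SAE a disposition category of its own, reported by dose.
5. State that these subjects remain in their cohort's DLT assessment and under the follow-up duty in 2(6). Membership of the safety set is already provided for.

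The cost is a rewording of two lists and one disposition code in the CRF. No visits, assessments or staff are added.

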Study design		Using a traditional "3+3" dose-escalation design, subjects will be sequentially assigned to one of three dose groups (2.8×10^{10} units, 1.4×10^{11} units, and 7.0×10^{11} units per dose, once daily, with continuous intranasal instillation for 4 days). Each dose group will include 3 subjects, who will be enrolled one by one. The exploration of the next dose can only proceed if no dose-limiting toxicity (DLT) is observed in the 3 subjects. If 1 out of the 3 subjects experiences DLT, an additional 3 subjects will be enrolled in the same dose group; the exploration of the next dose can only move forward if no DLT is observed in these newly added 3 subjects. A minimum of 6 and a maximum of 18 subjects will be recruited during the dose exploration phase. Patients will receive other standard medical treatments in accordance with the recommendations in the 2022 Chinese Guidelines for Secondary Prevention of Ischemic Stroke and Transient Ischemic Attack , including antiplatelet drugs or anticoagulants, antihypertensive drugs, lipid-lowering drugs, and glucose-lowering drugs.
Outcome Measures	Primary Outcome Measure	Dose-Limiting Toxicity (DLT) Related to hUC-MSC-sEV-001 Includes: (1) Grade 3-4 severe adverse events occurring on day 14 (+-2), graded according to Common Terminology Criteria for Adverse Events (CTCAE) V5.0; (2) NIHSS score increase of ≥ 4 from baseline on day 14 (+-2); NIHSS score assessed by a professional rehabilitation physician;(3) Symptomatic intracranial hemorrhage occurring on day 14 (+-2); detected via CT scan and patient symptom presentation.
	Secondary Outcome Measures:	Serious adverse events related to the investigational drug within 90 (+-7) days. Distribution of Modified Rankin Scale (mRS) Scores within 90 (+-7) days. Barthel Index within 90 (± 7) days. Five-level, five-dimensional EuroQol (EQ-5D-5L) . Proportion of Modified Rankin Scale (mRS) Scores of 0-2 within 90 (+-7) days. All-cause mortality at 90 (+-7) days. Changes in infarct volume at 14 (+-2) days compared to baseline. Change from Baseline in National Institutes of Health Stroke Scale (NIHSS) Score.
Follow-up duration		Baseline (0~1 day), 7 (± 1) days, 14 (± 2) days, 90 (± 7) days
Sample size		6-18 subjects need to be included.

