Single-center, prospective, dose-escalation clinical trial.

(2) Trial Administration Strategy

A traditional "3+3" dose-escalation design will be adopted. Subjects will be sequentially assigned to one of three dose groups (2×10^{10} units, 1×10^{11} units, 5×10^{11} units per administration, once daily for 4 consecutive days via intranasal instillation). Each dose group initially enrolls 3 subjects, with sequential enrollment (i.e., the next subject is enrolled only after the previous subject completes the 14-day DLT observation period).

- If no DLT is observed in 3 subjects of a dose group, the study proceeds to the next higher dose level.

- If 1 out of 3 subjects experiences DLT, an additional 3 subjects are enrolled in the same dose group. If no DLT is observed in the additional 3 subjects, the study proceeds to the next higher dose level; if ≥ 1 additional subject experiences DLT, the current dose level is defined as the maximum tolerated dose (MTD), and dose escalation is terminated.
- A total of 6 to 18 subjects will be recruited during the dose-escalation phase.

(3) Study Suspension or Early Termination

The study will be suspended or terminated early if any of the following occurs:

- Violation of the *Good Clinical Practice (GCP)* or the *Administrative Measures for Stem Cell Clinical Research (Trial)*;
- Emergence of new safety or efficacy data on MSC-sEVs indicating that the trial poses a serious risk to patient safety or is clearly ineffective;
- Failure to enroll subjects as scheduled for 3 consecutive months;
- Major protocol deviations that affect the validity of study data;
- Request for termination by the sponsor or regulatory authorities.

2. Subject Selection Criteria

(1) Inclusion Criteria

- Confirmed diagnosis of acute ischemic stroke (in accordance with the *Chinese Guidelines for the Diagnosis and Treatment of Acute Ischemic Stroke (2023)*);
- Aged 18-70 years, regardless of gender;
- Anterior circulation occlusion (internal carotid artery, middle cerebral artery M1/M2 segment) confirmed by CTA or MRA;
- mRS score of 0-1 before the current stroke episode (indicating no or minimal disability prior to the index event);
- ASPECTS ≥ 6 on non-contrast computed tomography (NCCT) or diffusion-weighted imaging (DWI) after stroke onset (indicating a small to moderate infarct volume);
- NIHSS score ≥ 6 at screening (indicating moderate to severe neurological deficit);

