1. Neurological Function Scales:

- **NIHSS:** Assesses the severity of neurological deficits (range: 0-42; higher scores indicate more severe deficits). Administered at baseline, Day 7, Day 14, and Day 90.
- **mRS:** Assesses functional independence (range: 0-6; scores 0-2 indicate good functional outcome). Administered at baseline, Day 7, Day 14, and Day 90.
- **Modified Barthel Index (MBI):** Assesses activities of daily living (range: 0-100; higher scores indicate better independence). Administered at baseline, Day 14, and Day 90.
- **EQ-5D-5L:** Assesses health-related quality of life (including mobility, self-care, usual activities, pain/discomfort, anxiety/depression; scored as a utility value ranging from -0.291 to 1.0). Administered at baseline, Day 14, and Day 90.

2. Cerebral Perfusion Parameters (CTP):

- Measured at baseline, Day 14, and Day 90: cerebral blood volume (CBV), cerebral blood flow (CBF), mean transit time (MTT), time to peak (TTP) in the infarct core and penumbra.
- Changes in perfusion parameters from baseline are used to evaluate the improvement of cerebral blood flow.

3. Infarct Volume Measurement:

- Infarct volume is measured on DWI using the ABC/2 method (A: maximum length, B: maximum width perpendicular to A, C: number of slices × slice thickness).
- Changes in infarct volume from baseline to Day 14 are used to evaluate infarct progression or regression.

5. Outcome Evaluation Indicators

(1) Primary Safety Endpoints

- **Dose-Limiting Toxicity (DLT):** Assessed within 14 days of the first dose, defined as any of the following:
 1. Grade 3-4 AE related to the study drug (CTCAE V5.0), such as severe nasal bleeding, anaphylactic reaction, or hepatic injury;
 2. Increase in NIHSS score ≥ 4 points from baseline (indicating significant neurological deterioration);
 3. Symptomatic intracranial hemorrhage (confirmed by CT/MRI and associated with neurological deterioration).

(2) Secondary Safety Endpoints

1. **SAE Incidence:** Proportion of subjects with drug-related SAEs within 90 days of the first dose;
2. **All-Cause Mortality:** Proportion of subjects who die from any cause within 90 days of the first dose;
3. **Laboratory Abnormality Rate:** Proportion of subjects with Grade ≥ 3 laboratory abnormalities (e.g., thrombocytopenia, elevated liver enzymes) within 90 days.

(3) Efficacy Endpoints

1. **Functional Outcome:** Proportion of subjects with mRS score 0-2 at Day 90;

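### A dosed subject whose stroke worsens must leave the study with no NIHSS required and no counting rule, so some DLTs can be missed; DLT item 1 also stops short of death

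*Protocol*

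**What the plan says.** **Withdrawal on worsening.** For a subject whose stroke deteriorates after dosing, Protocol section 2(4) states: "they shall withdraw from the study and be classified as an invalid case (not a lost-to-follow-up case". Progression of the deficit is given as an example, but no number of points and no period. The label appears nowhere else in the protocol and is tied to no analysis set, DLT count or replacement rule.

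**DLT definition.** Section 5(1) uses a window of 14 days from the first dose. Item 2 is: "Increase in NIHSS score ≥ 4 points from baseline (indicating significant neurological deterioration". Item 1 is limited to drug-related adverse events of Grade 3-4, and item 3 is symptomatic intracranial hemorrhage. The synopsis words item 2 as "NIHSS score increase of ≥ 4 from baseline on day 14 (+-2" and adds "NIHSS score assessed by a professional rehabilitation physician". Section 8(1) refers the DLT definition to section 5(1). Section 8(2) lists Grade 5 as death, separate from Grades 3 and 4.

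**Assessment after withdrawal.** Section 2(6): "the investigator shall conduct a final safety assessment (if possible) and document the reason for withdrawal in the CRF". For lost-to-follow-up subjects, section 2(4) asks every effort to "complete the final safety assessment (e.g., vital signs, adverse event recording" and so on. Neither place names NIHSS.

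**Escalation.** Section 1(2): "If no DLT is observed in 3 subjects of a dose group, the study proceeds to the next higher dose level". Enrolment is sequential: "the next subject is enrolled only after the previous subject completes the 14-day DLT observation period".

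**The concern.** Neurological worsening after dosing is what DLT item 2 exists to detect, and in section 5(1) that item carries no condition of relatedness. It is therefore the item that does not depend on the investigator's causality judgement. Section 2(4) sends the same subjects out of the study on any deterioration, possibly before a score shows whether the 4-point threshold was reached. A worsening of 2 or 3 points is enough to trigger withdrawal, and a later rise past 4 may never be scored.

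The DLT count is the only input to the 3+3 rule. In a cohort of 3, one missed DLT turns expansion into escalation (1 of 3 read as 0 of 3). It can also turn termination into expansion (2 of 3 read as 1 of 3), because section 2(7) ends the study at 2 or more DLTs at one dose level. This rule operates during enrolment, and the conflicting clause is protocol text, so a later analysis plan cannot repair it.

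The Grade 5 wording is a separate defect in the same definition: the most severe grade is left out of item 1.

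**Working it through.** **1. The plan's own figures.** The maximum of 18 reproduces as 3 dose levels × 6 subjects. The 90% and 80% probabilities in section 11(4) are given without DLT rates, so they cannot be reproduced. This point does not dispute them.

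**2. When a score exists.** Dosing is on Days 0-3 (section 3(2)). Post-baseline NIHSS relevant to the DLT window is scheduled at Day 7 (Days 6-8) and Day 14 (Days 12-16) (sections 4(3) and 6). A subject withdrawn before Day 6 may have no post-baseline NIHSS. Section 2(5) itself foresees subjects without one. Adverse event follow-up under section 8(6) may be in person, by telephone or by video according to severity, and no scale is required.

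**3. Which worsening is still counted under section 5(1).**

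| Situation within 14 days of first dose | Item | Counted as DLT? |
|---|---|---|
| Rise of 4 or more scored before withdrawal | 2 | Yes |
| Symptomatic intracranial hemorrhage | 3 | Yes |
| Worsening graded 3-4 and judged related | 1 | Yes, without an NIHSS |
| Not hemorrhagic; judged unrelated or below Grade 3; no rise of 4 scored before withdrawal | none | Only if a later NIHSS is taken, which nothing requires |
| Related death (Grade 5), no earlier qualifying event | none, literally | No |

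The fourth and fifth rows are the gaps.

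**4. What one missed DLT does to the decision.** Let p be the DLT rate in later subjects (assumed; the protocol gives none) and q = 1 − p. Rule: 0 of 3, escalate; 1 of 3, add 3 and escalate if none of these has a DLT; 2 or more, stop.

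*True count 1 of 3.*
- Counted: all 3 added subjects must be DLT-free, q³.
- Missed, subject replaced: the replacement is DLT-free (q), or has a DLT (p) and the expansion is clean (q³), giving q + p·q³.
- Missed, subject left in as DLT-free: 1.

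*True count 2 of 3.*
- Both counted: 0.
- One missed, subject replaced: replacement DLT-free, then a clean expansion, q·q³ = q⁴.
- One missed, subject left in: q³.

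| Chance of escalating | p = 10% | p = 20% | p = 33% (1/3) |
|---|---|---|---|
| 1 of 3, counted | 0.729 | 0.512 | 0.296 |
| 1 of 3, missed and replaced | 0.900 + 0.100 × 0.729 = 0.973 | 0.800 + 0.200 × 0.512 = 0.902 | 0.667 + 0.333 × 0.296 = 0.765 |
| 1 of 3, missed and left in | 1 | 1 | 1 |
| 2 of 3, counted | 0 | 0 | 0 |
| 2 of 3, one missed and replaced | 0.656 | 0.410 | 0.198 |
| 2 of 3, one missed and left in | 0.729 | 0.512 | 0.296 |

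A simulation of 400,000 runs agreed with the replaced rows to within 0.001. The figures assume that a DLT has already been missed, and they do not describe the Grade 5 gap.

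**The case against.** The protocol protects more than section 2(4) suggests.

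- An unscored NIHSS is not the same as an uncounted DLT, because item 1 catches related Grade 3-4 worsening without a score. This stands and confines the gap to the fourth row of the first table.
- Follow-up after an AE or SAE withdrawal continues until the event resolves or stabilises (section 2(6)), and SAE follow-up reports are due every 7 days (sections 8(3) and 8(5)). The contents of the final safety assessment are only examples. This stands too, but none of that text calls for an NIHSS or assigns a DLT status.
- Section 8(1) makes section 5(1) the governing DLT definition, so the synopsis tie to Day 14 should not prevail. Agreed; the synopsis wording is an inconsistency to tidy, not a route by which DLTs are lost.
- The invalid-case label can be read as concerning efficacy only, since section 2(5) deals with the efficacy set and keeps dosed subjects with safety data in the safety set. That reading is reasonable, but membership of the safety set does not say how the subject counts in a cohort of 3.
- The sequential rule requires completion of the 14-day period, which speaks against treating an early leaver as DLT-free. It makes the left-in rows less plausible without settling the matter: it governs when the next subject may enter, while escalation asks only that no DLT be observed.
- A related death would probably stop the study under sections 2(6) and 2(7) (causally suggestive SAEs, unexpected severe toxicity). That is likely, but those grounds are not the escalation rule.

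A reader might infer that every worsening subject drops out of the DLT count, or that escalation after a drug-related death is to be expected. The documents support neither.

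**Conclusion.** The point holds in a narrow form. Followed as written, section 2(4) can remove a subject before DLT item 2 is assessed, no text restores that assessment, and the 3+3 rule leaves the subject's status open. The loss is confined to worsening that is not hemorrhagic, is judged unrelated or below Grade 3, and has not been scored at 4 or more points before withdrawal. The Grade 5 omission is a literal defect in item 1 with probable, but not certain, cover elsewhere.

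The effect on one cohort decision is large if such a loss occurs, as the second table shows. Those probabilities rest on an assumed p and on a DLT already having been missed. It is tempting to read them as the trial's rate of wrong escalation, but how often a DLT would go unscored cannot be derived from the protocol, so no unconditional figure is available. The wording is still worth correcting, because the count governs subjects' exposure to higher doses and the correction is cheap.

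**What to change.** 1. **Section 2(4).** Delete the invalid-case clause. State that stopping study drug does not end follow-up, and let this govern the withdrawal wording in sections 3(4) and 8(3). Take an NIHSS at worsening or withdrawal and, unless consent is withdrawn, at the existing Day 14 visit.
2. **Section 5(1) and synopsis.** Define item 1 as a related adverse event of Grade 3 or higher, including Grade 5. Align the synopsis with the section 5(1) window of 14 days from the first dose.
3. **Section 1(2).** State that no subject with unknown DLT status counts as DLT-free for escalation. Such a subject is replaced unless the available data show a DLT.

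The NIHSS in step 1 does most of the work. Replacement alone would leave the missed-and-replaced probabilities in the second table, so it is only a fallback. Counting every deteriorating early leaver of unknown status as a DLT would be stricter, but natural stroke progression could then halt escalation; that is a debatable trade-off and is not needed here.

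Cost: protocol wording, one unscheduled NIHSS, an occasional replacement subject, and possibly slower escalation.
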